10.2.2 Collection and Rating of Adverse Events

All AEs, irrespective of the relatedness to the study drug, will be collected and reported on the Adverse Event Report Form from signature of the ICF through 30 days after the last dose of study drug. In case of an SAE, a Serious Adverse Event Report Form must be completed and transmitted to the sponsor or designee.

Overdoses and medication errors in the presence of clinical consequences should be recorded as AEs. The clinical consequence should be reported as “[enter AE] due to overdose”.

10.2.2.1 Onset Date

The onset date is the date when the first sign(s) or symptom(s) were first noted. For example, if the AE is an abnormal laboratory test (such as “platelets low”), the onset date is the date when the sample was taken. If the subject was hospitalized for meningitis, and symptoms such as fever, headache and nausea started the day before the hospitalization, the onset date is the day symptoms presented versus day of hospitalization.

10.2.2.2 Assessment of Intensity

Each adverse event will be graded according to the following definitions:

- **Grade 1 (Mild):** asymptomatic or mild symptoms; clinical or diagnostic observations only; intervention not indicated;
- **Grade 2 (Moderate):** minimal, local or noninvasive intervention indicated; limiting age-appropriate instrumental activities of daily living (ADL) [Instrumental ADL refer to preparing meals, shopping for groceries or clothes, using the telephone, managing money, etc];
- **Grade 3 (Severe):** medically significant but not immediately life-threatening; hospitalization or prolongation of hospitalization indicated; disabling; limiting self-care ADL [self-care ADL refer to bathing, dressing and undressing, feeding self, using the toilet, taking medications, and not bedridden]
- **Grade 4 (Life-threatening):** Life threatening consequences; urgent intervention indicated;
- **Grade 5 (Fatal):** death related to AE.

10.2.2.3 Relationship to Study Drug

The assessment of the relationship of an AE to the administration of study drug is a clinical decision based on all available information at the time of the completion of the CRF.

The causal relationship of the study drug to an AE will be rated as follows:

- **Related:** the AE has at least a possible or stronger causal relationship to the study drug, i.e., there are facts in evidence to suggest a causal relationship to the study drug. The study treatment and the AE are reasonably related in time, and any alternative etiology is equally or less likely.
- **NOT Related:** Exposure to study treatment did not occur; or the occurrence of the AE is not reasonably related in time, or is due to an underlying/intercurrent illness, or to other medication or procedure; or the AE is considered unlikely to be related to the study treatment.

10.2.2.4 Action Taken

The action taken toward the study drug in response to an AE will be listed as one of the following:

- **None:** no change in study drug dosage was made
- **Reduced:** dose of study drug was reduced, with or without a period of temporary suspension of dosing
- **Discontinued:** the study drug was permanently stopped

10.2.2.5 Outcome of Adverse Event

The outcome of an AE will be recorded as one of the following:

- **Recovered:** fully recovered or the condition has returned to the level observed at Baseline
- **Recovered with sequelae:** resulted in persistent or significant disability or incapacity; the nature of the sequelae should be specified
- **Not yet recovered**
- **Death**

10.2.3 Adverse Event Follow-up

Adverse events requiring therapy must be treated with recognized standards of medical care to protect the health and well-being of the subject.

Any subject who has any AE (whether serious or non-serious) or clinically significant (in the investigator's opinion) abnormal laboratory test values will be evaluated by the investigator or qualified designee and will be treated and followed up until the symptoms or values return to normal or acceptable levels, as judged by the investigator and the sponsor.

All AEs, whether serious or non-serious, will be collected beginning at the time of signing informed consent through 30 days after the last dose of study drug. All AEs should be followed until resolution or:

- 30 days from onset; or
- the subject is lost to follow-up (as defined in [Section 6.4.1](#)); or
- the subject withdraws consent,

whichever occurs first.

Any follow-up information available at the time of the subject's end of study will be included in the clinical study report.

10.3 Serious and Other Significant Adverse Events

10.3.1 Definition of a Serious Adverse Event

A serious adverse event is any adverse event that

- **Results in death.** Death is not an event per se but rather an outcome. Note that any adverse event resulting in a fatal outcome must be fully documented and reported, including deaths that occur within 30 days after treatment ends and irrespective of the causal relationship to the study drug.
- **Is life-threatening.** Life-threatening refers to an AE in which the subject was at immediate risk of death at the time of the event. It does not refer to an event, which may have caused death, if it was more severe.
- **Requires in-patient hospitalization or prolongation of existing hospitalization.** Hospitalization means that the subject was admitted to hospital or that existing

hospitalization was extended as a result of an adverse event. Hospitalization describes a period of at least 24 hours. Over-night stays for observation, stays at the emergency room or treatment on an out-patient basis do not constitute a hospitalization. However, medical judgment must always be exercised and, when in doubt, the case should be considered serious (i.e. if the case fulfills the criterion for a medically important event). Hospitalization for administrative or social purposes does not constitute an SAE. Hospital admissions and/or surgical operations planned before study inclusion are not considered AEs if the illness or disease existed before the subject was enrolled in the study, provided that the condition did not deteriorate during the study.

- **Results in persistent or significant disability/incapacity.** Disability/incapacity means a substantial disruption of a person's ability to conduct normal life functions. If in doubt, the decision should be left to medical judgment by the investigator.
- **Is a congenital anomaly/birth defect.** Any congenital anomaly or birth defect observed in any offspring of the subject conceived during treatment with the study drug.
- **Is an important medical event.** Important medical events are events that may not be immediately life-threatening or result in death or hospitalization but may jeopardize the subject or may require intervention to prevent one of the other outcomes listed in the definition above. Examples of important medical events include AEs that suggest a significant hazard, contraindication or precaution, occurrence of malignancy or development of drug dependency or drug abuse. Medical and scientific judgment should be exercised in deciding whether events qualify as medically important.

An AE caused by an overdose or medical error is considered serious if a criterion listed in the definitions above is fulfilled.

The following are not considered SAEs:

- A pre-existing condition that is present prior to or at the start of the study that did not worsen
- Hospitalizations for treatment which were elective or preplanned, for a pre-existing condition unrelated to the indication under study that did not worsen
- Admission to a hospital or other institution for general care, not associated with any deterioration in condition.

10.3.2 Serious Adverse Event Reporting by the Investigator to the Sponsor

Any SAE that occurs after a subject has entered the study, whether or not related to study drug, must be reported to the sponsor or the sponsor's agent immediately (within 24 hours) via telephone or e-mail. If initially reported via telephone, this must be followed-up by a written SAE report. The investigator must report all SAEs occurring from the time the subject signs the ICF until 30 days after last treatment with the study drug.

A completed Serious Adverse Event Report Form with the best possible details must be transmitted to the sponsor representative within 24 hours of knowledge of the SAE according to contact details as specified below:

Sponsor Representative and Contact Information for SAE Reporting:

SAE Reporting Primary Contact: Premier Research Pharmacovigilance

10.3.3 Handling of Follow-up Information

Follow-up information may be required or additional information may be requested by the sponsor (e.g., evolution of the SAE, other signs or symptoms, final diagnosis, final outcome, hospital discharge summary, or autopsy report). The same procedures and timelines as for initial reporting, listed above, should be followed for any follow-up information. If necessary, the study site will be visited to collect additional information.

Follow-up information is required on all SAEs until one the following criteria is satisfied:

- The final outcome of the case is known
- The event is resolved or the medical condition of the subject is stabilized
- No further information is available
- Sponsor assessment has been finalized
- The subject has withdrawn consent for further follow-up; information obtained up to the date and time of withdrawal of consent will remain a part of the study record.

10.3.4 Reporting and Follow-up of Pregnancy

When an investigator becomes aware of the pregnancy of a female subject (or female partner of a male subject), the investigator must withdraw the subject from the study treatment and follow the pregnancy until termination or until the child is 1 month old. The pregnancy will be reported immediately by telephone and by faxing a completed Pregnancy Report to the sponsor within 24 hours of knowledge of the event. The pregnancy will not be processed as an SAE; however, the investigator should notify the sponsor or the sponsor's agent of the outcome of the pregnancy by submitting a follow-up Pregnancy Report.

Additionally, if the outcome of the pregnancy meets the criteria for immediate classification of an SAE (e.g., spontaneous or therapeutic abortion, stillbirth, neonatal death, or congenital anomaly), the investigator will report the event by phone and by faxing a completed SAE Report Form to the sponsor within 24 hours of knowledge of the event.

10.3.5 Expedited Reporting of Serious Adverse Events

10.3.5.1 Responsibilities

The sponsor is responsible for ensuring the timely reporting of SAEs to regulatory authorities and all investigators who participate in the clinical development program of the study drug. It is the responsibility of the investigator to provide the sponsor with the case information such that reporting timeline demands of applicable regulatory authorities can be met.

10.3.5.2 Expedited Reporting

All AEs that are serious, unexpected, and considered related to the study drug judged by the sponsor will undergo expedited reporting. All available information relevant to the evaluation of the SAE will be reported. Serious adverse events will be considered reportable regardless of whether or not the study drug was used in accordance with the provisions in the protocol.

Adverse events which are serious, but expected, or those which are not associated with the study drug will only be subjected to expedited reporting if they are required to be reported to an authority according to national requirements.

10.3.5.3 Timelines

Fatal or life-threatening serious unexpected related cases require rapid reporting. regulatory authorities shall be notified as soon as possible but no later than 7 calendar days after first knowledge by the sponsor representative, followed by as complete a report as possible within 8 additional calendar days.

Serious unexpected related cases that are not fatal or life-threatening must be submitted as soon as possible, but no later than 15 calendar days after first knowledge by the sponsor representative that the case meets the minimum criteria for expedited reporting.

It is the responsibility of the investigator to support sponsor activities needed to meet the aforementioned timelines for regulatory authority reporting in the event of an SAE.

10.4 Safety Monitoring and Risk Mitigation Plan

Measures to minimize the risks to subjects enrolled in this clinical trial have been taken with respect to the following study design elements:

1. Subject safety and tolerability will be monitored in this study across multiple dimensions by tracking clinical adverse events; vital signs (including orthostatic pulse and blood pressure); general and neurological physical examinations; standard clinical laboratory safety panels for complete blood counts, chemistry, coagulation, and urinalysis; standard 12-lead electrocardiograms; and the Epworth Sleepiness Scale (ESS) and Columbia Suicide Severity Rating Scale (C-SSRS).
2. The specified inclusion/exclusion criteria have been carefully considered to avoid enrollment of subjects for whom exposure to the study drug might pose a hazard.
3. The anticipated subject population (with essential tremor) is acknowledged to likely be older than the healthy volunteer and schizophrenic populations that have previously undergone phase 1 and 2 study with CX-8998 (formerly MK-8998, Merck & Co, Inc). Since older male and female subjects may experience greater CX-8998 exposures than younger males on whom most of the existing PK data are based, this study will perform a careful dose titration in which dosing of CX-8998 will be initiated at 4 mg BID for 7 days, increasing to 8 mg BID for 7 days, and finally, if tolerated, to the target dose of 10 mg BID for 14 days. Subjects will return to the clinic for each dose up-titration for safety assessment. The study is designed to allow for flexible titration; should subjects experience intolerable AEs (see

[Section 10.2.1, Adverse Events, Definitions](#)) at 4 mg, 8 mg or 10 mg BID, the dose may be decreased to the previous lower dose (2 mg BID in the case of 4 mg BID). Subjects experiencing intolerable AEs at 2 mg BID will be discontinued from treatment.

4. Dose up-titration (e.g., from 4 mg BID to 8 mg BID) requires that the subject be evaluated in the clinic by the PI or sub-I. PI's and sub-I's may advise a subject to reduce or suspend their dose based on telephone elicitation of adverse events. During each clinic visit involving a dose up-titration, subjects will be observed and monitored in the clinic for at least 2 hours following the first administration of the increased dose step.
5. Dose modification and stopping rules are in place for individual subjects (see [Section 4.5, Dose Adjustments/Toxicity Management](#)). Near real-time safety and tolerability monitoring for individual subjects is the primary responsibility of the PI and sub-I's.
6. All serious adverse events (SAEs) meeting criteria for expedited reporting to the US FDA will be reported to the FDA and all IRBs in accordance with regulatory timelines.
7. The sponsor's study safety representative *and* a separate independent medically qualified and clinical trials-experienced safety monitor physician will monitor aggregate study level safety and tolerability on a recurring basis: The first review will occur after approximately 25% of the projected sample size of subjects have completed the EOS Visit and the second review will occur after approximately 50% of the projected sample size of subjects have completed the EOS Visit. These reviews will be based on blinded, select listings and summary tables of the evolving safety and tolerability data for each arm of the study. The sponsor's study safety representative and the independent safety monitor physician will review the blinded study data to determine if there is a sufficiently clinically significant difference between the blinded treatment arms in terms of frequency, severity, and/or seriousness of adverse events to take actions such as 1) unblinding specific safety data; 2) eliminating one or more of the planned dose up-titrations (e.g., not escalating from 8 to 10 mg BID); or 3) suspending new enrollment in the study until further safety review and consultation with the PI's and sub-I's can be performed. Decision-making will depend on the specifics of the safety and tolerability data reviewed. If the sponsor's study safety representative and/or the independent safety monitor physician decide that any data should be unblinded, then the unblinded data will be reviewed only by the independent safety monitor physician.
8. In the event of a treated subject's death within 30 days of the last dose of study drug and that is assessed by the treating PI/sub-I or the independent safety monitor physician or the study safety representative as at least possibly related to study drug, further enrollment into the study will be immediately suspended until a safety review can be conducted by the independent safety monitor physician, the study safety representative, the actively participating PIs and sub-Is, and the sponsor. As required by regulation, all deaths meeting criteria for expedited reporting to the US

FDA will be reported to the FDA and all IRBs within regulatory timelines. A final decision to re-open the study to new enrollment without modification(s), re-open with modification(s), or terminate the study will be made by the overall study principal investigator, the independent safety monitor physician, and the sponsor's study safety representative.

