4.3 Administration

CX-8998 (or placebo) will be administered as 4 mg (2 capsules) twice daily (8 mg/d) in the first week; increasing to 8 mg (4 capsules) BID (16 mg/d) in week 2, to a target of 10 mg (5 capsules) BID (20 mg/d) in weeks 3 and 4.

Treatment compliance will be assessed based on return of unused drug.

Subjects experiencing specified adverse events will have their dose adjusted. See [Section 4.5](#) for details on dose adjustments.

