25. AEs will be collected from signature of the ICF through 30 days after the last dose of study drug [\(Section 10.2.2\)](#). Adverse events will be followed for resolution in accordance with [Section 10.2.3](#).
26. The first dose of study drug at each dose level will be administered in the clinic. Subjects will be instructed to eat breakfast. At Visits 2, 3, and 4 subjects should hold their morning dose, as their dose will be administered in the clinic after the subject has undergone the first set of orthostatic VS and required pre-dose PK sampling, and/or has been evaluated by the investigator for suitability to undergo specified dose increase. Subjects will remain under observation for a minimum of 2 hours post dosing prior to discharge at Visits 1, 2 and 3, or the time that is required to complete all of the required procedures for the visit [\(Section 4.3\)](#).
27. Subjects will initiate dosing at 4 mg (2 capsules) administered twice daily with food. After 7 days dosing, the dose will be increased to 8 mg (4 capsules) twice daily, per subject tolerance. After 7 days at 8 mg BID, the dose will be increased to 10 mg (5 capsules) twice daily, per subject tolerance (Section 4.3.).
28. Compliance will be assessed via pill counts. [\(Section 4.4.\)](#)

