7.2.2 Visit 1 (Day 1 - Baseline)

Subjects will return to the clinic within 28 days of screening (or 42 days in the case of those with extended screening due to discontinuation of primidone.) Following confirmation of continued eligibility and randomization, subjects will undergo safety and efficacy assessments as detailed in Table 3 and will then receive their first dose of study drug (4 mg of CX-8998 or placebo). Subjects will be followed for adverse events for at least 2 hours after dosing. Orthostatic VS and triplicate ECGs will be obtained 1 to 2 hours after dosing. The investigator or qualified designee will make the determination whether it is safe to release the subject from the clinic. Subjects will be instructed to take the second daily dose of study drug no closer than 10 hours and no later than 14 hours (every 12 hours \pm 2 hours) from the time of their first dose, and to continue taking 4 mg (or placebo) twice daily for the following week (see Administration details in [Section 4.3](#)).

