7.2.3 Visit 2 (Day 8 – End of Week 1)

Subjects will return to the clinic for assessments as detailed in Table 3. Subjects will have withheld their morning dose of study drug.

If the subject has been at least 75% compliant with the study drug regimen (as detailed in [Section 4.4](#)) and has not experienced any intolerable adverse events (as described in [Section 4.5](#)), the dose of study drug will be increased to 8 mg (or placebo) twice daily for the following week. If compliance is determined to be less than 75%, up-titration should be discussed with the study safety representative.

Subjects will receive the first 8 mg dose of study drug (or placebo) and will then undergo safety assessments. Subjects will be followed for adverse events for at least 2 hours prior to discharge. Orthostatic VS and triplicate ECGs will be obtained 1 to 2 hours after dosing. The investigator or qualified designee will make the determination whether it is safe to release the subject from the clinic. Subjects will be instructed to take the second daily dose of study drug no closer than 10 hours and no later than 14 hours (every 12 hours \pm 2 hours) from the time of their first dose, and to continue taking 8 mg (or placebo) twice daily for the following week (see Administration details in [Section 4.3](#)).

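### Visit 2 and Visit 3 windows both count from Day 1, so the stated 7 days at 8 mg BID can shrink to 3 before the step to 10 mg

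*Protocol*

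**What the plan says.** The current protocol version (about 106 subjects, target dose 10 mg BID) gives the length of the 8 mg step in several places.

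- Section 10.4, item 3, presents the titration as a precaution because older subjects may have greater exposure: "dosing of CX-8998 will be initiated at 4 mg BID for 7 days, increasing to 8 mg BID for 7 days", followed by 10 mg BID for 14 days if tolerated.
- Table 3, note 27, words it as a dosing instruction, subject to tolerance: "After 7 days dosing, the dose will be increased to 8 mg (4 capsules) twice daily", and then "After 7 days at 8 mg BID, the dose will be increased to 10 mg (5 capsules) twice daily".
- Section 4.3 puts the 8 mg dose in a single week: "increasing to 8 mg (4 capsules) BID (16 mg/d) in week 2".

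The timing of the steps is set elsewhere.

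- Table 3 places Visit 2 at Day 8 (±2), Visit 3 at Day 15 (±2) and Visit 4 at Day 28 (-1).
- Each step is taken at a visit. Table 3, note 26, says: "The first dose of study drug at each dose level will be administered in the clinic". Sections 7.2.3 and 7.2.4 give the first 8 mg dose at Visit 2 and the first 10 mg dose at Visit 3.
- The conditions for stepping up in 7.2.3 and 7.2.4 are compliance ("If the subject has been at least 75% compliant with the study drug regimen") and no intolerable adverse event. Neither section names a minimum number of days on the current dose.

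**The concern.** For an ordinary assessment visit, a ±2-day window is harmless. Here the visit is the dose increase, so the gap between Visits 2 and 3 is the time spent at 8 mg. Because each window is anchored to Day 1 and not to the preceding step, lateness at Visit 2 adds to earliness at Visit 3, and up to 4 of the 7 days can be lost without any visit being out of window. At such a Visit 3 a site that follows 7.2.4 raises the dose, while a site that follows note 27 does not. The protocol does not say which governs.

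Time on each dose is one of the protocol's own risk measures, since 10.4 offers the titration as its answer to possibly higher exposure in older subjects. An early step is also not freely reversible: Section 4.5 allows one dose-step reduction and no re-titration upward, and it requires discontinuation if intolerable events recur.

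**Working it through.** **Inputs.** First 4 mg dose on Day 1 (7.2.2). Visit 2 on Days 6 to 10, Visit 3 on Days 13 to 17, Visit 4 on Day 27 or 28 (Table 3). First 8 mg dose at Visit 2 and first 10 mg dose at Visit 3 (7.2.3, 7.2.4).

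**Formulas.** Days at 4 mg = Visit 2 day − 1. Days at 8 mg = Visit 3 day − Visit 2 day. Titration time before 10 mg = Visit 3 day − 1.

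**The plan's own figures.** On the nominal days, 8 − 1 = 7 at 4 mg and 15 − 8 = 7 at 8 mg, as stated.

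**Days at 8 mg over the permitted windows.**

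| Visit 2 day | Visit 3 Day 13 | Day 14 | Day 15 | Day 16 | Day 17 |
|---|---|---|---|---|---|
| 6 | 7 | 8 | 9 | 10 | 11 |
| 7 | 6 | 7 | 8 | 9 | 10 |
| 8 | 5 | 6 | 7 | 8 | 9 |
| 9 | 4 | 5 | 6 | 7 | 8 |
| 10 | 3 | 4 | 5 | 6 | 7 |

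The range is 3 to 11 days. Below 7 there are 0 + 1 + 2 + 3 + 4 = 10 of 25 pairs: four at 6 days, three at 5, two at 4 and one at 3.

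**Other limits.** Days at 4 mg run from 6 − 1 = 5 to 10 − 1 = 9. The 3-day stay at 8 mg follows 9 days at 4 mg. Visit 3 is never before Day 13, so at least 13 − 1 = 12 days of titration precede 10 mg.

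**Does the compliance rule prevent a short step?** Section 4.4 defines non-compliance as missing more than 25% of the doses required between visits. With twice-daily dosing, a 3-day gap holds 2 × 3 = 6 doses, so a subject who took all six is fully compliant. Section 4.4 also lists a Week 2 minimum of 11 of 14 doses, stated per 7 days. If that were read as an absolute floor, gaps of 3, 4 and 5 days (6, 8 and 10 doses) would fall short, but a 6-day gap (12 doses) would pass. Four of the ten short pairs survive even that reading.

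**The case against.** The strongest reply is that 7, 7 and 14 days are nominal figures and the windows are their tolerance. The 14 days is itself not exact: with Visit 3 on Day 15 and the last dose on the morning of Day 28, a subject takes 2 × 13 + 1 = 27 doses at 10 mg, while Section 4.4 counts 28. A window permits early and late days but does not require them. A Visit 2 on Days 8 to 10 with Visit 3 at least 7 days later satisfies every rule, and six of the 25 pairs do so for both steps. The extreme of 3 days is one pair, it follows 9 days at 4 mg, and it precedes a 25% increase, not the doubling from 4 to 8 mg.

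Much of this stands. It disposes of the 4 mg step: 5 or 6 days after an early Visit 2 is ordinary scheduling tolerance. A reader might count both steps together and infer that 19 of 25 pairs break the titration, or that sites cannot follow the protocol. The documents do not support either inference. The 19 includes those mild 4 mg cases, and compliant schedules exist.

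The reply does not dispose of the 8 mg step. A tolerance of 2 days on each visit becomes a tolerance of 4 days on the interval between them, and no text shows that this was intended. Note 27's reference to tolerance lets an investigator hold a dose back; it does not say how long the previous dose must last.

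**Conclusion.** The point holds for the 8 mg step and is minor. The protocol states 7 days at 8 mg BID before 10 mg, but its visit rules permit as few as 3, and 10 of 25 permitted day pairs give fewer than 7. How often short steps would occur is not in the documents; it would be zero if every subject kept the same weekday.

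Two larger conclusions might be inferred and should not be.

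- **Biased efficacy result.** Assignment is randomised and blinded, both arms follow the same visit rules, and the Day 28 time point is unaffected.
- **Harm to subjects.** The pharmacokinetic text and most of the dose rationale are not visible, so the effect of a short step on tolerability cannot be judged. In-clinic evaluation, two hours of observation and dose reduction still apply.

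What remains is a stated safeguard that the schedule does not secure. The conclusion rests on reading Section 4.4 as a rate; on the floor reading the shortest qualifying stay at 8 mg is 6 days and the gap is smaller.

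**What to change.** State in Table 3 and Section 7.2.4 that Visit 3 takes place no earlier than 7 days after the actual Visit 2 date and no later than Day 17. Keep Visit 2 at Day 8 (±2) and Visit 4 at Day 28 (-1). Add to note 27 that the 7 days at 4 mg is nominal, subject to the Visit 2 window.

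**Cost.** Amendment wording and one visit-window check, with no extra visits or subjects. Scheduling is tighter: for Visit 2 on Days 6, 7, 8, 9 and 10 there remain 5, 4, 3, 2 and 1 permitted days for Visit 3, or 15 of the 25 pairs. A Day 10 Visit 2 leaves only Day 17.

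Time at 10 mg before Visit 4 falls a little. Weighting permitted days equally (an assumption), mean Visit 3 moves from Day 15.0 to (75 + 62 + 48 + 33 + 17)/15 = 235/15 = Day 15.67. With mean Visit 4 at Day 27.5, mean time at 10 mg goes from 12.5 to 11.83 days. The range stays at 10 (27 − 17) to 15 (28 − 13).

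**Alternatives.** Saying only that the windows prevail would remove the inconsistency at no cost but would leave the 3-day case open. Forbidding an early Visit 2 as well would secure 7 days on both steps, but it leaves six day pairs and lowers mean time at 10 mg to 11.2 days, further from the 14 days that 10.4 states. That is a trade-off for the sponsor and is not needed to settle this point.
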